9.2.7 Insomnia Severity Index (ISI)

The ISI is a 7-item self-report questionnaire assessing the nature, severity, and impact of insomnia. The usual recall period is the "last month" and the dimensions evaluated are: severity of sleep onset, sleep maintenance and early morning awakening problems, sleep dissatisfaction, interference of sleep difficulties with daytime functioning, noticeability of sleep problems by others, and distress caused by the sleep difficulties. A 5-point Likert scale is used to rate each item (i.e. 0 = none; 4 = very severe). The categorical responses are slightly different for some of the questions, but the numeric scores remained the same from 0 to 4. If all questions are answered, then the total score will be calculated by the sum of all the responses ranging from 0 to 28. If any of the 7 questions are missing, then the total score will be set to missing. The total score is interpreted as follows [17, 18]:

- Absence of Insomnia (0-7)
- Sub-Threshold Insomnia (8-14)
- Moderate Insomnia (15–21)
- Severe Insomnia (22–28)

The secondary endpoints of interest with this data is the total score change from baseline to Week 2 and Week 4. Subjects will be instructed to answer each question based their sleep patterns in the last 2 weeks, so responses should be interpreted as cumulative over that time period. The ISI will be assessed at the Baseline, Week 2, and Week 4/Early Termination visits.

The total score actual means and change from baseline will be summarized using descriptive statistics. ANCOVA analyses using the mean change from baseline will be provided for individual models for Weeks 2 and 4. The change from baseline to last post-baseline visit for each subject will also by summarized. The 4 interpreted total score categorical values will be summarized in a frequency distribution table and a shift table.

9.2.8 Hospital Anxiety and Depression Scale (HADS)

The HADS is a self-reported screening tool for anxiety and depression in non-psychiatric clinical populations. The scale consists of 14 items (7 each for anxiety and depression), each rated on a 4-point scale ranging from 0 to 3 (i.e. 0 = not at all; 3 = most of the time). The categorical responses are slightly different for some of the questions, but the numeric scores remained the same from 0 to 3. Responses are based on the relative frequency of symptoms over the preceding week^[19].

When a HADS questionnaire is partially incomplete, the individual subscale scores are estimated by assuming that the missing item(s) have a value equal to the average of those in existence, provided that no more than 3 items of a subscale are missing [20]. The individual imputed missing scores will use the specific subscale mean score and will be rounded off to the nearest whole number. If an individual subscale score is missing 4 or more items, then that subscale score will be set to missing. A total score adding the anxiety and depression subscale scores for HADS will not be calculated.

Possible scores range from 0 to 21 for each subscale. An analysis of scores on the 2 subscales supported the differentiation of each mood state into 4 ranges^[21]:

- Normal Cases (Scores 0-7)
- Mild Cases (Scores 8-10)
- Moderate Cases (Scores 11-14)
- Severe Cases (Scores 15-21)

The secondary endpoints of interest with this data is the published subscale and total scores change from baseline to Week 4. Subjects will be instructed to answer each question based how they have felt in the past week, so responses should be interpreted as cumulative over that time period. The HADS will be assessed at the Screening, Baseline, and Week 4/Early Termination visits.

The actual means and change from baseline will be summarized using descriptive statistics. ANCOVA analyses using the mean change from baseline will be provided for Week 4. The change from baseline to last post-baseline visit for each subject will also by summarized. The 4 interpreted categorical values for each subscale will be summarized in a frequency distribution table and a shift table.

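### Rounding each imputed HADS item before summing adds avoidable error to the subscale score: at most 0.5, 0.8 or 1.5 points with 1, 2 or 3 items missing

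*SAP*

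**What the plan says.** SAP 9.2.8 describes the instrument as follows: "The scale consists of 14 items (7 each for anxiety and depression), each rated on a 4-point scale ranging from 0 to 3". For incomplete forms it estimates the subscale by "assuming that the missing item(s) have a value equal to the average of those in existence", and allows this "provided that no more than 3 items of a subscale are missing". Beyond that limit there is no imputation: "If an individual subscale score is missing 4 or more items, then that subscale score will be set to missing".

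The sentence after the averaging rule adds the step at issue: "The individual imputed missing scores will use the specific subscale mean score and will be rounded off to the nearest whole number". Rounding is therefore done on each imputed item, before the seven items are summed.

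The resulting scores feed descriptive statistics and an ANCOVA of change from baseline to Week 4, plus frequency and shift tables on four bands (0-7, 8-10, 11-14, 15-21). In SAP Section 13, Tables 14.2.8.1, 14.2.8.2 and 14.2.8.4 are marked for the topline analyses.

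**The concern.** The averaging rule and the rounding step give different scores. HADS items are whole numbers, and the mean of 4, 5 or 6 of them usually is not. Once rounded, the imputed item no longer equals the average that the preceding sentence prescribes. All missing items in a subscale take the same imputed value, so their rounding errors do not cancel; they add.

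The SAP also does not say how a mean ending in .5 is rounded. Two programmers following the text could produce different scores from the same form.

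At stake is extra noise, and possibly a small shift, in a continuous secondary endpoint. The ANCOVA does not need whole-number scores. The SAP avoids intermediate rounding elsewhere: the SF-MPQ-2 total (9.2.5) is averaged from unrounded scale scores, and the BPI-DPN composites (9.2.10) are means of the available items, rounded only at the end.

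**Working it through.** **Inputs (all SAP 9.2.8).** Seven items per subscale, each scored 0 to 3; at most 3 imputed; imputed value = mean of the observed items, rounded to a whole number.

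**The plan's own figure.** 7 x 0 = 0 and 7 x 3 = 21, which reproduces the stated subscale range.

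**Formulae.** Let k items be missing and S be the sum of the 7 - k observed items.
- Score under the averaging rule: S + k x S/(7 - k) = 7 x S/(7 - k).
- Score under the SAP rule: S + k x round(S/(7 - k)).
- Error: k x [round(S/(7 - k)) - S/(7 - k)].

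**Largest error, from every possible S.**

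| Missing | Observed | Worst observed mean | Observed sums | Largest absolute error |
|---|---|---|---|---|
| 1 | 6 | ends in .5 | 3, 9, 15 | 1 x 0.5 = 0.5 |
| 2 | 5 | ends in .4 or .6 | 2, 3, 7, 8, 12, 13 | 2 x 0.4 = 0.8 |
| 3 | 4 | ends in .5 | 2, 6, 10 | 3 x 0.5 = 1.5 |

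These maxima hold under both half-up and half-to-even rounding.

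**Worked forms with 3 items missing.**
- Observed 0, 1, 0, 1: mean 0.5, averaging rule 7 x 0.5 = 3.5. Half-up gives 2 + 3 x 1 = 5; half-to-even gives 2 + 3 x 0 = 2. The tie rule alone moves this form by 3 points.
- Observed 1, 2, 1, 2: mean 1.5, averaging rule 7 x 1.5 = 10.5. Both conventions give 6 + 3 x 2 = 12.

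**Average error with 3 items missing.** The observed mean ends in .00, .25, .50 or .75. Under half-up rounding the errors are 0, -0.75, +1.5 and +0.75. If the four endings were equally likely, the average would be (0 - 0.75 + 1.5 + 0.75)/4 = +0.375, and one form in four would be off by 1.5. Under half-to-even, ties at 0.5 and 2.5 go down and ties at 1.5 go up, so the sign depends on where scores lie. In simulations with assumed item means of 0.6 to 1.5, the average error is about +0.25 to +0.4 with half-up and about -0.3 to +0.1 with half-to-even. With equal weight on every possible sum, half-up gives an average of about +0.08 for 1 missing item and 0 for 2.

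**Accuracy against the true subscale total.** In simulations of 3 missing items with assumed, positively correlated items, the root mean square error is 1.1 to 1.6 for the unrounded score and 1.45 to 1.85 for the rounded one. The unrounded score was closer in every scenario run.

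**Change scores.** If both visits have imputed items, errors can combine. Under half-up rounding the worst case is +1.5 (3 missing at one visit) against -0.8 (2 missing at the other): 1.5 + 0.8 = 2.3 points. Under half-to-even it is 1.5 + 1.5 = 3.0.

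**Severity bands.** For every S and k, the SAP score was compared with the total 7 x S/(7 - k) rounded once, half-up. No band changes under half-up item rounding. For example, S = 6 with 3 missing gives 12 against 11 (10.5 rounded), both in the 11-14 band.

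**The case against.** The rounding is a stated step, part of a SAP that is to be final before unblinding (4.6), and it applies alike to every arm. It can be read as how the averaging rule is carried out, and it has a plausible purpose: HADS items are whole numbers and the bands are defined only for whole numbers. The unrounded score is itself only an estimate. The rule cites a source that is not available here, so whether that source rounds is unknown. This stands: a reader might infer that the section contradicts itself or that the scores are simply wrong, but the documents show a disclosed choice that departs from the averaging rule.

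A reader might also infer a general upward bias. That needs half-up rounding, which the SAP does not state; under half-to-even the average can be negative. Nor is 1.5 points a typical error. It needs exactly 3 of 7 items missing and an observed sum of 2, 6 or 10, and some incomplete forms have no rounding error at all.

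The effect on a group mean is probably very small. If 5% of forms had exactly 3 missing items (an assumption), the half-up shift would be 0.05 x 0.25 to 0.05 x 0.4, or about 0.01 to 0.02 points on a 0-21 scale. A similar shift would be expected in each arm, and would partly cancel in change from baseline.

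What the objection does not supply is a benefit from item-level rounding. The bands can be assigned by rounding the total once, and the ANCOVA needs no rounding.

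**Conclusion.** The point holds as a minor improvement. Item-level rounding adds avoidable error of at most 0.5, 0.8 or 1.5 points with 1, 2 or 3 items missing; these bounds are exact and need no distributional assumption. The average-bias figures do rest on assumptions (3 items missing, item means of 0.6 to 1.5, and a tie rule the SAP omits), so no direction of bias can be attributed to the plan as written.

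Only incomplete HADS forms are affected, and the documents give no rate for them, so the practical effect cannot be computed. The primary endpoint is untouched. Under half-up rounding the frequency and shift tables do not move. Nothing in the documents supports a reading that a trial conclusion is at risk.

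**What to change.** In SAP 9.2.8, delete the item-level rounding and state: when at most 3 items of a subscale are missing, the subscale score is 7 times the mean of the observed items. Use this score unrounded in the descriptive statistics and the ANCOVA. For the four category ranges only, round the final subscale score to a whole number, with halves rounded up, and say so.

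The cost is about one sentence and one line of code, with no change to data collection. Each imputed subscale will have an unrounded value for analysis and a rounded one for the bands, so the dataset specification should name both. Because SAP 5.3.1 ties the decimals of the minimum and maximum to the recorded data, the display precision for these scores should be stated as well. The change should be made before database lock.

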9.2.9 Daily Sleep Interference Scale (DSIS)

The collection method of the Daily Sleep Interference Scale (DSIS) score has data that is similar to the primary efficacy data described in Section 9.1 for the NRS score assessing average pain intensity in the past 24 hours. However, the study days are shifted by one day based on the analysis visits described in Section 5.4.3 due to the scores are based on sleep from the previous study day:

- Baseline (average of Study Days -6 to 1)
- Week 1 (average of Study Days 2 to 8)
- Week 2 (average of Study Days 9 to 15)
- Week 3 (average of Study Days 16 to 22)
- Week 4 (average of Study Days 23 to 29)

Daily collected scores and are based on an 11-point numerical rating scale/Likert scale ranging from 0 to 10. Where 0 represents "did not interfere with sleep" and 10 is "completely interfered with sleep/unable to sleep" due to pain^[23].

The secondary endpoints of interest with this data is the change in the mean score from baseline to each analysis week of treatment (Weeks 1, 2, 3, and 4). The same analyses methods will be applied to the Daily Sleep Interference Scale (DSIS) score as described in Sections 9.1, 9.1.1 and 9.1.2. No imputation methods for missing data will be applied for these secondary endpoints.

The actual means and change from baseline at each analysis visit will be summarized using descriptive statistics. ANCOVA analyses using the mean change from baseline will be provided for individual models for Weeks 1, 2, 3, and 4 as described in Section 5.3.5.2. A MMRM model will be analyzed for all post-baseline analysis visits (Weeks 1, 2, 3, and 4) for the mean change from baseline as described in Section 5.3.5.3.

9.2.10 Brief Pain Inventory for Diabetic Peripheral Neuropathy (BPI-DPN)

The BPI is a patient-completed numeric rating scale that assesses the severity of pain (Severity scale), its impact on daily functioning (Interference scale), and other aspects of pain (e.g., location of pain,

relief from medications). A modified version of the BPI, including the 4-item pain Severity scale (Worst Pain, Least Pain, Average Pain, and Pain Now) and the 7-item pain Interference scale (General Activity, Mood, Walking Ability, Normal Work, Relations with Others, Sleep, Enjoyment of Life) has been validated in patients with painful diabetic peripheral neuropathy, which distinguishes between pain due to DPN and pain due to other causes. Each BPI item uses a 0 to 10 numeric rating scale anchored at zero for "no pain" and 10 for "pain as bad as you can imagine" for Severity, and "does not interfere" to "completely interferes" for Interference^[24].

If at least 3 of the 4 Severity items have a reported score, then the Pain Severity Index will be the calculated mean. Otherwise, the Pain Severity Index will be set to missing. If at least 4 of the 7 Interference items have a reported score, then the Pain Interference Index will be the calculated mean. Otherwise, the Pain Interference Index will be set to missing. The Pain Severity Index and the Pain Interference Index will be referred to as composite scores^[25].

The study-issued handheld devices were not programmed with logic checks to flag instances in which subjects might have mistakenly reported their worst pain intensity scores as being less than their average pain intensity scores. However, rather than assume these to be self-evident errors and thus correct them, such scores will be analyzed based on the actual values collected. Also, the least pain in the last 24 hours scores may be greater than the worst pain in the last 24 hours and/or right now pain scores. Edit checks were not applied in the handheld devices for the subject's confusion of the three scores. The Pain Severity Index score equally distributes all these three scores and the average pain score. Therefore, the Pain Severity Index score is not impacted by any of these scores being transposed. As a result the scores will be analyzed based on the values collected.

The 2 composite scores will take on values ranging from 0 to 10 and will be rounded off by one number after the decimal point. A total pain score for BPI-DPN will not be calculated.

The secondary endpoints of interest with this data is the 2 composite scores change from baseline to Week 4. Subjects will be instructed to answer each question based their pain at the time or within the last 24 hours. The BPI-DPN will be assessed at the Baseline and Week 4/Early Termination visits.

The actual means and change from baseline will be summarized using descriptive statistics. ANCOVA analyses using the mean change from baseline described in Section 5.3.5.2 will be provided for individual models for Week 4. The change from baseline to last post-baseline visit for each subject will also by summarized.

BPI-DPN question 8, "In the last 24 hours, how much relief have pain treatments or medications provided? Please circle the one percentage that most shows how much relief you have received." will be collected on the CRF and has values that range from 0% (no relief) to 100% (complete relief). This question will be included in the descriptive statistics, but not in the ANCOVA analyses.

BPI-DPN question 1, "Throughout our lives, most of us have had pain from time to time (such as minor headaches, sprains, and toothaches). Have you had pain other than these everyday kinds of pain today?" is a categorical response (yes/no). This data will be presented in a subject listing, but not summarized in a table.

BPI-DPN question 2, "On the diagram, shade in the areas where you feel pain. Put an X on the area that hurts the most." will be provided in subject listings, be not in any summary tables. BPI-DPN question 7, "What treatments or medications are you receiving for your pain?" was not collected in the eDT because this was included in the prior and/or concomitant medications collected on the CRF.

9.3 Exploratory Efficacy Endpoints

9.3.1 Use of Rescue Medication Subgroup Analyses

Boxplots will be produced for each treatment arm side-by-side for the mean change from baseline NRS scores assessing average pain intensity in the past 24 hours versus the average rescue medication taken (g/day) at the following analysis visits:

- Baseline (average of Study Days -7 to -1)
 - o Versus Rescue Medication from Screening to Baseline
- Week 1 (average of Study Days 1 to 7)
 - o Versus Rescue Medication from Baseline to Week 2
- Week 2 (average of Study Days 8 to 14)
 - o Versus Rescue Medication from Baseline to Week 2
- Week 3 (average of Study Days 15 to 21)
 - Versus Rescue Medication from Week 2 to Week 4
- Week 4 (average of Study Days 22 to 28)
 - Versus Rescue Medication from Week 2 to Week 4

Scatter plots will also be produced for each analysis listed above for the mean change from baseline NRS scores assessing average pain intensity in the past 24 hours versus the average rescue medication taken (g/day).

Daily rescue medication taken will be collected in the daily diary data for each subject. If a subject recorded the use of rescue medication, then the NRS score for that specific day will be set to the mean baseline value calculated for the NRS scores assessing average pain intensity in the past 24 hours. Otherwise, the individual NRS scores assessing average pain intensity in the past 24 hours will remain the same value as collected. As an additional exploratory analysis, mean NRS score assessing average pain intensity in the past 24 hours will be recalculated for the post-baseline analysis visits described in Section 5.4.2:

- Week 1 (average of Study Days 1 to 7)
- Week 2 (average of Study Days 8 to 14)
- Week 3 (average of Study Days 15 to 21)
- Week 4 (average of Study Days 22 to 28)

ANCOVA analyses using the mean change from baseline will be provided for Weeks 1, 2, 3, and 4 as described in Section 5.3.5.2. These results compared to the analyses stated in Sections 9.1.2 and 9.2.2 will assist in determining the impact use of rescue medication.

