that is being discontinued. The only allowed analgesic for painful diabetic peripheral neuropathy may not be an *N*-methyl-D-aspartate receptor ligands, must be non-opioid and non-sedative, and must not interfere with subjects' pain reporting (Section 8.7). The allowed analgesics must have been taken for at least 1 month (30 days) prior to Visit 1, and subjects must be on a stable fixed dose that is not expected to change during the study.

The discontinuation of all (but 1 allowed, as applicable) analgesic medications will be managed by the principal investigator at the investigative site. Subjects already taking no more than 1 allowed concomitant analgesic medication at Visit 1 may directly begin Week -1 of the Screening Period.

Subjects will be dispensed acetaminophen to be used as rescue medication, and will be instructed to take no more than 2 g/daily (one to two 500-mg caplets every 4 to 6 hours as needed) for DPN pain.

Beginning immediately after Visit 1, pain intensity and rescue medication use will be recorded in the study-issued handheld device daily at bedtime. Subjects will enter their average pain intensity, worst pain intensity, pain on walking, and whether rescue medication was used during the past 24 hours. Pain intensity will be recorded using an 11-point NRS, with 0 being no pain and 10 being the worst pain imaginable. Every morning upon awakening, subjects will complete the DSIS via their study-issued handheld device.

Screening Period (Week -1)

The investigative site staff will contact study subjects by telephone weekly through Week -1 to reinforce the reporting instructions (i.e., diary completion) and to assess adverse events. Subjects will be asked a non-leading question to inquire about potential adverse events, "Have you experienced any new or changed symptoms since we last asked/since last week?" Subjects taking no more than 1 allowed concomitant analgesic medication at Visit 1 may directly begin Week -1 of the Screening Period.

Baseline (Week 0, Visit 2)

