9.1 Primary Efficacy Data

The primary efficacy data for this study is the NRS score assessing average pain intensity in the past 24 hours. Daily collected pain scores are based on an 11-point numerical rating scale/Likert scale ranging from 0 to 10. Where 0 represents no pain and 10 is the worst pain imaginable^[2].

The mean NRS score assessing average pain intensity in the past 24 hours will be calculated for the analysis visits described in Section 5.4.2^[4]:

- Baseline (average of Study Days -7 to -1)
- Week 1 (average of Study Days 1 to 7)
- Week 2 (average of Study Days 8 to 14)
- Week 3 (average of Study Days 15 to 21)
- Week 4 (average of Study Days 22 to 28)

The mean baseline visit will be calculated if at least 6 of the study days have a reported pain score. This is a requirement in order to be eligible for being randomized to a study drug treatment arm. There will need to at least 4 daily pain scores collected within a post-baseline analysis visit in order to calculate the mean pain score for that visit.

Each mean analysis visit score will take on values ranging from 0 to 10 and will be rounded off by one number after the decimal point. Data prior to Study Day -7 or after Study Day 28 will not be used in the mean calculated scores. No missing data imputations will be used for these observed means, but Section 9.1.3 will explain imputation methods used for sensitivity analyses.

The actual means, change from baseline, and percent change from baseline at each analysis visit will be summarized using descriptive statistics. The same descriptive statistics table will be additionally provided by each study site, age groups, gender, race, ethnicity, and subjects using or not using at least 1 concomitant analgesic medication at Baseline. All data collected and derived will be presented in subject listings.

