14.2.1.2.2	Efficacy	Table: Analysis of Covariance Model for Mean Change from Baseline NRS Score Assessing Average Pain Intensity in the Past 24 Hours (Model-Based Missing Data Imputation)
14.2.1.2.3	Efficacy	Table: Analysis of Covariance Model for Mean Change from Baseline NRS Score Assessing Average Pain Intensity in the Past 24 Hours (LOCF Missing Data Imputation)
14.2.1.2.4	Efficacy	Table: Analysis of Covariance Model for Mean Change from Baseline NRS Score Assessing Average Pain Intensity in the Past 24 Hours (BOCF Missing Data Imputation)
14.2.1.2.5	Efficacy	Table: Analysis of Covariance Model for Mean Change from Baseline NRS Score Assessing Average Pain Intensity in the Past 24 Hours (BOCF Rescue Medication Data Imputation)
14.2.1.2.6	Efficacy*	Table: Analysis of Covariance Model for Mean Change from Baseline NRS Score Assessing Average Pain Intensity in the Past 24 Hours (Concomitant Analgesic Medications)
14.2.1.3.1	Efficacy	Table: Mixed Effects Repeated Measures Model for Mean Change from Baseline NRS Score Assessing Average Pain Intensity in the Past 24 Hours
14.2.1.3.2	PP	Table: Mixed Effects Repeated Measures Model for Mean Change from Baseline NRS Score Assessing Average Pain Intensity in the Past 24 Hours
14.2.1.4.1	Efficacy*	Table: Responder Status Endpoints Based on Mean NRS Score Assessing Average Pain Intensity in the Past 24 Hours
14.2.1.4.2	Efficacy	Figure: Percentage-Reduction from Baseline at Week 4 for Mean NRS Score Assessing Average Pain Intensity in the Past 24 Hours
14.2.1.5.1	Efficacy	Table: Number of Days to Responder Status Based on Mean NRS Score Assessing Average Pain Intensity in the Past 24 Hours
14.2.1.5.2	Efficacy	Figure: Probability of Number of Days to Responder Status Based on Mean NRS Score Assessing Average Pain Intensity in the Past 24 Hours
14.2.1.6.1	Efficacy	Table: Number of Days to Sustained Pain Reduction Based on Mean NRS Score Assessing Average Pain Intensity in the Past 24 Hours
14.2.1.6.2	Efficacy	Figure: Probability of Number of Days to Sustained Pain Reduction Based on Mean NRS Score Assessing Average Pain Intensity in the Past 24 Hours
14.2.1.7.1	Efficacy	Figure: Boxplots of Weekly Mean Change from Baseline NRS Score Assessing Average Pain Intensity in the Past 24 Hours and Average Rescue Medication Taken (g/day)

Number	Population*	TFL: Title

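### The rescue-day substitution in SAP 9.3.1 also overwrites scores worse than baseline, so a subject who worsened and took rescue can be recorded as unchanged or improved

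*SAP*

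**What the plan says.** SAP 9.3.1 gives the rule in two sentences. If rescue use was recorded, "then the NRS score for that specific day will be set to the mean baseline value". For all other days, "Otherwise, the individual NRS scores assessing average pain intensity in the past 24 hours will remain the same value as collected". The only trigger is recorded rescue use. Nothing in 9.3.1 or elsewhere limits the replacement to scores better than baseline.

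The status is exploratory: "As an additional exploratory analysis, mean NRS score assessing average pain intensity in the past 24 hours will be recalculated". The recalculated weekly means go into the ANCOVA of 5.3.5.2 for Weeks 1 to 4. Set against the analyses of 9.1.2 and 9.2.2, the results "will assist in determining the impact use of rescue medication". SAP Section 13 lists the output as Table 14.2.1.2.5, labelled "BOCF Rescue Medication Data Imputation".

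The inputs are collected daily. Protocol 6.1 has subjects enter "whether rescue medication was used during the past 24 hours" at bedtime together with the pain scores. SAP 9.1 gives the scale: "Daily collected pain scores are based on an 11-point numerical rating scale/Likert scale ranging from 0 to 10". The primary analysis in 9.1.2 keeps the recorded scores on rescue days.

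**The concern.** Scoring a rescue day at baseline is understandable when the recorded score is below baseline, because some of that improvement may come from the acetaminophen. When the recorded score is above baseline, the same step replaces a valid observation of worsening with no change. A subject who worsens and takes rescue every day is recorded as exactly zero change.

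This differs from the baseline-carried-forward method in SAP 9.1.3, which fills missing scores. Here an observed score is overwritten. It also sits awkwardly with SAP 9.2.1, which keeps even implausible diary entries as collected.

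Rescue is taken as needed for neuropathy pain, so rescue days may well be the high-pain days. At stake is the reading of the only model-based rescue analysis in the SAP; the other rescue outputs are descriptive summaries and plots. If the difference shrinks against 9.1.2, a reader may attribute the loss to rescue when it comes from the scoring rule.

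**Working it through.** **The plan's own figure.** SAP 4.4 assumes a difference of 1.05, SD 2.25 and 75 per group. SE = 2.25 × √(2/75) = 0.37. Two-sided power at 0.05 is 81.5% (normal) or 81.0% (t), which agrees with the stated 80% or so. The simulations below use these inputs.

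**One week, baseline mean 6.0.** This step needs no trial-level assumption.
- Rescue days worse than baseline: four non-rescue days at 5, three rescue days at 8. Observed: (4×5 + 3×8)/7 - 6 = +0.29. SAP rule: (4×5 + 3×6)/7 - 6 = -0.57. Higher of observed and baseline: +0.29.
- Rescue days better than baseline: four non-rescue days at 3, three rescue days at 5. Observed: (4×3 + 3×5)/7 - 6 = -2.14. SAP rule and higher-of rule: (4×3 + 3×6)/7 - 6 = -1.71.

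So the SAP rule penalises rescue on good days and rewards it on bad ones.

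**Effect on the treatment difference.** Let r be the share of rescue days in an arm and m the mean change from baseline on those days. The rule changes an arm's mean by -r×m, so the difference (active minus placebo) shifts by r_P×m_P - r_T×m_T. The documents give neither r nor m.

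Two checks by hand, with rescue unrelated to pain and mean changes of -1.5 and -2.55:
- 30% rescue in both arms: 0.30×(-1.5) - 0.30×(-2.55) = +0.32, toward zero.
- 50% placebo and 20% active: 0.50×(-1.5) - 0.20×(-2.55) = -0.24, away from zero.

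**Simulation.** 200,000 subjects per arm, Week 4, ANCOVA on baseline. Assumed, not in the documents: baseline mean about 6.3, within-subject daily SD 1.2, and the placebo changes and rescue shares shown. Rounding and clipping to the 0–10 scale lowers the observed difference from 1.05 to about 0.96. The last two columns split the total shift exactly: SAP rule minus higher-of rule is the part from above-baseline days; higher-of rule minus observed is the part from the other rescue days. Positive means toward zero.

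| Assumed scenario | Rescue days P / A | Of these above baseline P / A | Observed | SAP rule | Higher-of | Above-baseline part | Remainder |
|---|---|---|---|---|---|---|---|
| Strongly pain-driven, placebo -1.5 | 28% / 18% | 71% / 60% | -0.96 | -0.79 | -0.96 | 0.17 | 0.00 |
| Strongly pain-driven, placebo 0 | 45% / 33% | 83% / 75% | -0.96 | -0.61 | -0.95 | 0.34 | 0.01 |
| Moderately pain-driven, placebo -1.5 | 31% / 23% | 53% / 39% | -0.97 | -0.78 | -0.93 | 0.15 | 0.04 |
| Unrelated to pain, placebo -1.5 | 30% / 30% | 27% / 16% | -0.95 | -0.67 | -0.73 | 0.06 | 0.22 |
| Unrelated to pain, placebo -1.5 | 50% / 20% | 27% / 15% | -0.97 | -1.22 | -1.38 | 0.16 | -0.41 |
| Pain-driven, less rescue on active, placebo -2 | 41% / 12% | 39% / 38% | -0.95 | -1.10 | -1.27 | 0.17 | -0.32 |
| Unrelated to pain, placebo -1.5 | 20% / 50% | 27% / 15% | -0.97 | -0.04 | -0.02 | -0.02 | 0.95 |

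The rule also shrinks the residual SD, from about 2.1 to 1.5–1.8. In a further scenario (31% rescue days on placebo, 11% on active) the difference fell from -0.96 to -0.90 while power rose from 0.81 to 0.87. P-values can therefore move for a reason unrelated to rescue.

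**Bias of the higher-of rule.** For a subject with no true change and normal daily scores of SD 1.2, the expected excess of the larger of score and mean over the mean is 1.2 × 0.399 = 0.48. Simulation with whole-number scores gives 0.52. So a daily rescue user with no true change is recorded as about 0.5 points worse; the SAP rule records about 0.

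**The case against.** The strongest case against has four parts.

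First, a reader might infer that the rule necessarily dilutes the treatment difference, or always flatters the weaker arm. The documents do not support that. Two of the scenarios above moved the difference away from zero. With assumed changes of -1.2 and -2.25 and pain-driven rescue on 27–31% of placebo and 22% of active days, the placebo change went from -1.19 to -1.12 under moderate pain-dependence (looks worse) and from -1.20 to -1.28 under strong (looks better). Active looked worse in both. This part stands: the most that can be said is that the rule can dilute.

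Second, 9.3.1 never says that its purpose is to remove credit for relief from rescue, and the table label declares a baseline-carried-forward convention applied as named. That is fair on intent. It does not repair the rule: the comparison is still offered as evidence on the impact of rescue, and overwriting recorded worsening does not serve it.

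Third, the higher-of rule has its own upward bias. Rescue is also dispensed at Visit 1, so the baseline mean may already include rescue use; a subject using rescue equally before and after could then be scored as deteriorating. This stands, and is why neither version should be reported alone.

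Fourth, the consequence is limited. The analysis is exploratory, and rescue is also shown by plots and by summaries of grams per day. This stands, and sets the weight of the point.

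**Conclusion.** The defect is in the rule as written: recorded scores above baseline on rescue days are erased, and a worsened subject can appear unchanged or improved. That conclusion rests on the text and on arithmetic alone.

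Its effect on the trial-level comparison is conditional. Under strongly pain-driven rescue the difference lost 0.17 to 0.35 points, about 0.5 to 0.9 of the standard error of 0.37, nearly all of it from above-baseline days. Under moderate pain-dependence above-baseline days gave 0.15 of a 0.19-point loss. With rescue unrelated to pain and equal in both arms they gave only 0.06 of 0.28; the rest was the substitution's ordinary effect. Compared with the higher-of rule, the SAP rule gave a smaller difference in every scenario run except the one with more rescue on active. That is not the comparison the SAP makes, so it should not be read as dilution against the observed analysis. All these sizes rest on the assumed inputs.

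Nor should the point be read as a threat to the primary result, which uses recorded scores throughout. It is a worthwhile, inexpensive correction to an exploratory analysis.

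**What to change.** In SAP 9.3.1, on rescue days use the higher of the observed score and the subject's baseline mean, and leave other days as recorded. Keep the present baseline substitution as a second version and show the two side by side in Table 14.2.1.2.5 with the observed-data results.

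Add a small table by arm and week of rescue days with scores above, and at or below, the baseline mean. It supplies the information needed to see why the versions differ.

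State the limits in the text: the higher-of rule pushes noisy scores upward, baseline may already reflect rescue use, and a change in the treatment difference under either version is not by itself the effect of rescue.

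The cost is one condition in the derivation, one more ANCOVA run per week and one count table. The daily rescue indicator and pain score are already collected, and the edit can be made when the SAP is finalised before database lock.
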